Vrije Universiteit Brussel; [name] – Faculteit Lichamelijke Opvoeding en Kinesitherapie.

4) Sponsor:

This research is financed by the VUB Chair ‘Andullation Care Research’, represented by the investigators (cfr. point 3) and

- International Association of Andullation Technology (IAAT) - [name] (president dr. [name])
- Home Health Product bvba (HHP) – [name] (CEO [name])

5) Departments/laboratories involved in the study:

Universitair Ziekenhuis Brussel; [name]

- Medical Oncology ([name]. [name])
- Radiotherapy (Prof. dr. [name])
- Breast Clinic (Prof. dr. [name])

6) Introduction:

The (breast) cancer population in Belgium is growing due to increasing prevalence and decreased mortality, thanks to evolutions in diagnostics and treatment of cancer. More breast cancer patients survive and live with the complications of cancer and its treatment. That is why quality of life of this big group of chronic patients has become more important in the past decade(s). Bio-psychosocially as well as economically and financially, the whole Western World is struggling with a lack of options to monitor these patients with long-term effects and late effects of breast cancer and its treatment. Therefore, there is an active search for ways to prevent complications and facilitate self-management for these cancer survivors with negative side effects.

With this study, we address the breast cancer patient and not the breast cancer survivor in the first place. Our hypothesis is that a lot of complications can be prevented when acting proactively at the start of treatment. From recent research, we know that monitoring complications during chemotherapy results in higher survival rates for example. (Basch E. et al., 2017) The comfort of the patient during treatment will result in a more positive outcome, for example because there is a better therapy adherence and compliance. This will lead to faster rehabilitation and reintegration, less work absenteeism and other psycho-socio-economical disadvantages.

Physical and mental comfort of the patient during treatment is co-determined by (di)stress of diagnosis and treatment with its consequences like f.e. pain. From previous research, we know that the autonomic nervous system and more specifically the vagal nerve plays an important role in

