Group 2 (control group) will follow the same intervention protocol as group 1, but without the application of the Andullation® technology. Environmental parameters will be equal to those of group 1.

Producer/distributor

Producer:

International Association of Andullation® Technology (IAAT) - [name] (president dr. [name]) www.iaat.eu

Official dealer:

Home Health Product bvba (HHP) – [name] (CEO [name]) www.hhp.be

Packaging/storage conditions

Normal packaging, transport and storage conditions.

Known side effects

Up to now, there are no negative side effects reported about 20 minutes of Andullation® technology in literature or clinical experience. The Andullation® application is approved as a medical device by TÜV Rheinland Belgium N.V. and FDA massage mattress VM9100RM.

Pregnancy, epilepsy and a recent orthopaedic implant are contra indications reported by the producer and dealer.

Side effects will be registered during the trial.

9) The subjects:

Number of subjects

At the Department of Radiation Therapy of the UZ Brussel, an average of 8 breast cancer patients starts radiation therapy for about 3 to 5 weeks every week. Taking into account the sample size estimation/calculation, the duration of the project (Chair ‘Andullation Care Research’ of the VUB) and the availability of the medical device(s), we have constructed the inclusion schedule below (table 1).

The schedule is based on a 5-week intervention (and control) over a duration of 14 months to include 118 patients for the two study arms. If patients who have only 3 weeks of intervention are included, even more patients can be included. Therefore, insurance is based on the inclusion of maximum 130 patients, taking into account extra (3-week intervention) patients and a drop-out of 10%.

	M1/M2									start/2M	N = (op M14)
	W1	W2	W3	W4	W5	W6	W7	W8	W9		
1st week intervention	2	2	2	2	2	2	2	2	2	18	118
2nd week intervention		2	2	2	2	2	2	2	2		
3rd week intervention			2	2	2	2	2	2	2		
4th week intervention				2	2	2	2	2	2		
5th week intervention					2	2	2	2	2		
interventions/day	2	4	6	8	10	10	10	10	10		
	M13/M14										
	W53	W54	W55	W56	W57	W58	W59	W60	W61		
1st week intervention	2	2	2	2	2						
2nd week intervention	2	2	2	2	2	2					
3rd week intervention	2	2	2	2	2	2	2				
4th week intervention	2	2	2	2	2	2	2	2			
5th week intervention	2	2	2	2	2	2	2	2	2		
interventions/day	10	10	10	10	10	8	6	4	2		

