Questionnaire		- Distress Thermometer	- Brief Pain Inventory (BPI) - Numeric Pain Rating Scale (NRS)		- Pittsburgh Sleep Quality Index (PSQI) - Insomnia Severity Index (ISI)	- EORTC QLQ BR23

Measurement moment	Before, during and after each intervention	Baseline After each 3 rd intervention Follow-up	NRS: Before and after each intervention, Follow-up BPI: baseline, after each 3 rd intervention and follow-up	Baseline After 3 weeks After 5 weeks (if radiation lasts 5 weeks) Follow-up	Baseline After 3 weeks After 5 weeks (if radiation lasts 5 weeks) Follow-up	Baseline After 3 weeks After 5 weeks (if radiation lasts 5 weeks) Follow-up
--------------------	--	--	--	--	--	--

Table 2: Procedures of the study.

[figure not shown]

Figure 1: These measurements will be repeated in week 3 and if your radiation therapy has a duration of more than 3 weeks, these measurements will also be repeated in week 5.

Questionnaires

- Distress Thermometer
A questionnaire to evaluate in what extent the patient experiences complaints like distress and anxiety, on a visual thermometer. (Mitchell et al., 2007)

- EORTC QLQ BR23
A questionnaire designed to investigate the quality of life in breast cancer patients. (Michels et al., 2013)
- Brief Pain Inventory
This questionnaire was designed to investigate the extent of pain and the influence of it on quality of life. (Abahussin et al., 2018)
- Pittsburgh Sleep Quality Index (PSQI)
This questionnaire was designed to assess sleep quality, quantity and disturbance. (Beck et al., 2004)
- Insomnia Severity Index (ISI)
This questionnaire was designed to assess the severity, nature and impact of insomnia over the past two to four weeks. (Morin et al., 2011)

Body parameters

- ANSWatch®
A device measuring heart rate through skin sensors. With the information withdrawn, the device calculates heart rate variability. (Sun et al., 2011)
- Perometer®
A device measuring arm contours with the use of infrared light. It is an efficient, safe, painless and reliable method to examine arm volumes. (Adriaenssens et al., 2013)
- Bioimpedance
By using bioimpedance, body composition will be estimated. Patients have to stand on scale and hold on to a handgrip that is connected with the scale. A small current will determine the body composition and especially extracellular fluid. This is a painless and innocuous examination. (Seward et al., 2016)

11) Flowchart

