Inclusion (and intervention) will start from the moment we receive a positive advice of the Medical Ethical Comité and will last for 14 months. The project (VUB Chair) is assigned for 24 months in total. An MD will refer patients as potential candidates for the trial after screening of the inclusion criteria and during the intervention, there will always be at least one MD in the PR4 building. (cfr table 1 and figure 2)

12) Randomisation/blinding:

The patients will be randomized using the Efron's biased coin design. (Efron, 1971) Patients are stratified by duration of radiation therapy (3 weeks vs. 5 weeks), type of surgery (mastectomy vs.

breast conserving surgery and axillary lymph node dissection vs. sentinel node biopsy), and chemotherapy sequence (none vs. sequential vs. concomitant chemotherapy).

Blinding is not possible.

13) Prior and concomitant therapy:

The patients are allowed to use every medication needed for their treatment before, during and after the intervention.

Any medication that has an influence on HRV activity, sleep, stress, edema and pain are reported before intake in the trial and monitored throughout the study.

14) Study analysis:

Sample size calculation

Based on our calculation in G*Power (with a medium effect size of 0.5 and with a power = 0.8), the total sample size is 128.

[figure not shown]

Figure 5: Sample size calculation

Analysis of the samples and statistical analysis

The promotor and researcher of the VUB Chair will analyze the samples and do the statistical analysis.

For all statistical analyses, superiority will be based on a two-sided p-value < .05. All statistical computations use SPSS v. 20.0 (IBM Corporation, Somers, NY, 10589, USA). Descriptive statistics will be used to describe medical and demographic characteristics of the population. Normality and homogeneity for both groups will be calculated. The repeated measures ANOVA design will be used to evaluate the changes over time and between groups. Correlations between outcome measures will be calculated as well.

15) Quality control and quality assurance:

The researcher will be present when the intervention is given to install the patient, to start the intervention and to make sure that everything runs according to plan.

The researcher will also make sure that all settings are properly programmed and placed as indicated in the protocol prior to welcoming the patient. The researcher will use the same checklist before starting each intervention.

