Related to the quality control and assurance of the outcome measures:

- Each participant will have a form fill to list every data.
- All measurements are conducted by the same investigator and the same validated measurement instruments.
- All interventions are performed with the same medical device.

16) Publication policy:

Scientific and marginal publications will be possible within the academic freedom of the researchers and there are no restrictions concerning the other (industrial) partners of the VUB Chair.

A signed agreement of the Chair can be obtained at VUB TechTransfer ([name]) Contracts Administration [name].

17) All documents are confidential. These documents are only accessible to the treating doctor and to the persons concerned in the execution and control of this clinical study. The name and every information that could reveal patients' identity will not be used in publications arising from this study and will not be shared with third parties. The data will be processed according the principles imposed by the new European General Data Protection Regulation (GDPR), that is operative since May 25th 2018. In the context of the study certain personal data will be collected. We, [name] and [name], are responsible for the correct processing and the information duty that is required.

Of course, we are only allowed to use personal data for the scientific purposes described in the information consent document. It is possible that the data are seen by persons in countries that do not use the same norms in the field of legal protection of data as in the EU. In that case, we commit to ensure that the requirements of the European and Belgian legislation about the protection of personal data are respected.

Thereafter we would like to announce that, conform the relevant legislation, the data obtained in this study will be saved during at least 4 years. According to the GDPR there are

certain rights in the processing of the data. The data protection officer of the VUB can be contacted: [contact]

References:

All references related to Andullation® technology: <http://www.iaat.eu/science/>

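### The researcher who sets up and starts every session is also one of the two named analysts, and no masking of the analysis is planned while the primary HRV choices are still open

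*Combined protocol and SAP*

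**What the plan says.** Section 14 (analysis of the samples and statistical analysis) assigns the work to two roles jointly: "The promotor and researcher of the VUB Chair will analyze the samples and do the statistical analysis".

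Section 15 (quality control and quality assurance) describes the researcher's part in the sessions: "The researcher will be present when the intervention is given to install the patient, to start the intervention", and "The researcher will also make sure that all settings are properly programmed and placed as indicated in the protocol". It also says: "All measurements are conducted by the same investigator and the same validated measurement instruments". It does not say which role that investigator holds.

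Section 12 (randomisation/blinding) disposes of masking in one sentence: "Blinding is not possible". It does not distinguish patient, operator, assessor and analyst. Section 14 does not mention masking.

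Under section 8 (composition and dosing), the control group "will follow the same intervention protocol as group 1, but without the application of the Andullation® technology". In Table 2 of section 10, the primary outcome, heart rate variability, is taken "Before, during and after each intervention".

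**The concern.** It is credible that the patient, and the person who switches the vibration on or leaves it off, cannot be masked. That does not carry over to the analysis, which can be run on a file where the arms appear only as A and B. The plan does not provide for this, and one of its two analysts has set up the sessions.

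Masking the analyst adds little when every analytic decision is fixed in advance. Here many are not. Someone who knows the arms could choose the HRV index, drop a noisy recording, transform the data or decide which ANOVA term counts. Any of these can move the primary result without intent. Section 4 adds a reason for care over credibility: it says "This research is financed by the VUB Chair" and lists the association and the company that section 8 identifies as the device's producer and dealer among those representing the Chair.

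**Working it through.** **The plan's own figure.** Section 14 gives a total of 128 for effect size 0.5 and power 0.8. With a two-sided t-test at 0.05 and equal arms (the ratio is assumed, since none is stated), the requirement is 63.77, so 64 per arm and 2 × 64 = 128; power at 64 per arm is 0.8015. The figure reproduces. None of its inputs depends on who analyses or on whether arms are coded, so the change proposed below leaves it as it is.

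**Who knows the arm.** The arms differ in whether the vibration runs (section 8). The researcher programs the settings and starts the session (section 15), so the researcher knows the arm. Section 14 names the researcher as an analyst. One of the two analysts is therefore unmasked.

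**Who measures.** A single investigator takes all measurements (section 15), but section 3 lists a promotor, a coordinator and a research collaborator under that heading. The researcher is the likely person, because HRV is recorded around every session and the researcher is there. The text does not settle it.

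**Who could be masked.** The promotor is the other named analyst. The documents do not say who runs the biased-coin allocation, who holds it, or whether the promotor sees it.

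**What is left open in the primary analysis.**
- Index: sections 2 and 10 name vagal nerve activity measured by HRV, but no HRV parameter.
- Reading: three readings per session and three sessions a week give 3 × 3 × 3 = 27 occasions per patient over 3 weeks and 3 × 3 × 5 = 45 over 5 weeks. No primary time point or summary is named.
- Exclusions: no rule for poor or missing recordings.
- Model: a repeated measures ANOVA, without saying which effect decides superiority, and no action if the normality or homogeneity checks fail.

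**What each part of a remedy does.** A two-sided p-value comparing two arms is unchanged when the labels A and B are swapped. Coding alone therefore does not stop an analyst from trying several indices and keeping the smallest p-value; written pre-specification does that. Coding guards against decisions steered towards a known arm, such as which recordings to drop. The two measures do different jobs, and most of the protection here comes from the first.

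**The case against.** The case against is that the plan contains no contradiction or arithmetic error on this point, that analyst masking is good practice of unmeasured benefit, and that once the endpoint is pre-specified little is left for masking to do. The device calculates HRV itself (section 10), a checklist precedes each session, and section 16 leaves the researchers free to publish without restriction from the industrial partners. Most of this stands. Device calculation and the checklist limit bias in capturing HRV; they do not limit bias in selecting, excluding or transforming readings afterwards. Coding may also be partly defeated if the vibration leaves a visible trace in recordings made during a session.

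A reader might also infer more than the text supports:
- *That the researcher takes every reading.* Likely, but not stated. If the promotor is the measurer, the promotor is not masked either.
- *That the promotor could analyse masked with no extra staff.* Section 15 says the researcher is present, not that nobody else is. Section 3 gives the promotor roles at the same hospital, so contact with participants cannot be ruled out.
- *That the plan declares a masked analysis impossible.* The sentence stands in section 12; section 14 is silent.
- *That the bias can be sized by a multiple-testing formula.* Such a formula describes picking among endpoints, which coding alone does not reduce.
- *That the funding shows bias.* It bears only on how credible a positive result will look.

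**Conclusion.** The concern holds in a limited form. An analyst who knows each patient's arm, no planned masking of the analysis and an open primary analysis together allow choices that affect the primary result to be made with the arms visible. The one sentence on blinding does not justify this. It is an avoidable weakness and cheap to remove; it does not make the trial invalid.

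The size of the bias cannot be derived from the documents, and no figure is offered. The conclusion assumes that the researcher in section 15 is the same role as the Chair's researcher in section 14, and that the design figure, which was not available to check, adds nothing on masking. Whether the promotor can serve as masked analyst remains open until the sponsor states who measures and who holds the allocation.

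**What to change.** In section 12, limit the blinding statement to patients and the session researcher, and state who takes the measurements and who holds the allocation.

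In section 14:
- Fix the HRV index, the time point, the rules for excluding recordings and the SPSS syntax, including the effect that decides superiority, in writing before any outcome data are linked to arm.
- Apply exclusions by that rule, without reference to arm.
- Have the promotor, provided they have no part in sessions, measurement or allocation, run the primary analysis on a file with arms coded A/B and no session notes.
- Let the already unmasked researcher hold the code, which is opened once the result is recorded.

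If the promotor turns out to be exposed to allocation, keep the freeze before linkage and report the lack of masking as a limitation.

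The cost is a few sentences, one coded export and a freeze date. The drawback is that the session researcher does not run the confirmatory analysis. Sample size, alpha, power, visits and patient care are unaffected.

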The primary outcome measure of the autonomic nervous system is vagal nerve activity, a modulator of the parasympathetic nervous system. Vagal nerve activity plays an important role in subjective (patient reported) sensations of pain, (di)stress and edema (Koenig J et al., 2016; De Couck et al., 2014; Adriaenssens et al., *article in progress*) (secondary outcome measures), three common complications of breast cancer and its treatment. These three negative side effects may be risk factors for sleeping disorders in this population. Our hypothesis is that vagal nerve activity may directly influence sleeping disorders in this population without the presence of stress, pain and/or edema as well. (Werner et al., 2015) The relations between the parameters are shown in Figure 1.

The second reason for choosing this intervention, the application of Andullation® technology, is socio-economically. The whole western world is searching for self management strategies to help this big growing population of chronic patients, that can no longer be followed up close in the long run in standard hospital care.

[figure not shown]

Figure 1: Hypothesis of the relations between the intervention and the outcome measures.

3) Investigator(s):

Promotor: [name]. [name]

Universitair Ziekenhuis Brussel; [name]

- Oncologisch centrum: coördinator Oncological Rehabilitation and responsible for Cancer Survivorship at the UZ B
- Lymfekliniek: responsible of conservative treatment, consultant

Vrije Universiteit Brussel; [name] – Faculteit Lichamelijke Opvoeding en Kinesitherapie

- vakgroep KIMA, unit KINE – docent Revalidatiewetenschappen en Kinesitherapie
- research group Rehabilitation Research – Head of research line 'vascular pathology and oncology'
- President of the Postgraduate course 'Vascular Pathology and Oncology' at VUB
- General Secretary of the Belgian Society of Lymphology

Coordinator: [name]. Dr. [name]

Vrije Universiteit Brussel; [name] – Faculteit Lichamelijke Opvoeding en Kinesitherapie

- vakgroep KIMA, unit KINE – Gewoon Hoogleraar emeritus Revalidatiewetenschappen en Kinesitherapie
- co-founder of the European Society of Lymphology

- winner of the Europa Donna award by Queen Mathilde of Belgium
- winner of the Hilde Breurs award by the Vrije Universiteit Brussel

Research collaborator (Master of Science - Rehabilitation Sciences and Physical Therapy):
[name]

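### Superiority may be claimed at p < .05 in any analysis, but the plan does not fix which heart rate variability contrast decides the primary question

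*Combined protocol and SAP*

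**What the plan says.** Section 2 ranks the outcomes: "The primary outcome measure of the autonomic nervous system is vagal nerve activity, a modulator of the parasympathetic nervous system". Table 2 in section 10 labels the autonomic nervous system primary and stress, pain, edema, sleep and quality of life secondary.

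The primary measurement is HRV by a wrist device. Its description does not say which HRV parameter is meant: "With the information withdrawn, the device calculates heart rate variability". Table 2 schedules it "Before, during and after each intervention". Section 8 plans three sessions a week for three to five weeks.

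The inferential plan in section 14 is short. The decision rule is "For all statistical analyses, superiority will be based on a two-sided p-value < .05". The model is given in one sentence: "The repeated measures ANOVA design will be used to evaluate the changes over time and between groups". Correlations between outcomes are added. The sample size rests on a G*Power calculation "with a medium effect size of 0.5 and with a power = 0.8), the total sample size is 128"; the figure showing it is not reproduced in the text available.

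On who sees what, section 12 says "Blinding is not possible", and section 14 says "The promotor and researcher of the VUB Chair will analyze the samples and do the statistical analysis".

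**The concern.** A 5% rule controls the error of one test. Here it is attached to every analysis, and the primary outcome can yield many tests. Several HRV indices, three phases, up to 15 sessions and at least two ANOVA effects that involve group could each be presented as the primary result. If more than one of them may carry the claim, the chance of a false superiority finding exceeds 5%.

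The candidates also answer different questions. A difference present only while the mattress vibrates is not the same finding as a sustained shift between sessions. The stated aim, to study an influence on the autonomic nervous system, fits both, so it does not select one. Because allocation is open and the trial's own team does the analysis, nothing in the plan ensures that the choice is made before results by arm are visible.

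**Working it through.** **1. The plan's own figure.** Inputs from section 14: d = 0.5, power 0.8, two-sided .05. Equal allocation is assumed, since no ratio is stated. The two-sample t-test needs 63.77 per arm, so 64 per arm and 128 in total, with power 80.1%. A one-sided test would give 102. The stated 128 therefore fits one two-sided, two-group comparison.

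**2. Number of primary readings.** 3 sessions × 3 weeks = 9 sessions and 9 × 3 phases = 27 readings. 3 × 5 = 15 sessions and 15 × 3 = 45 readings. These counts are for one index only.

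**3. Either of two ANOVA effects may decide.** If the group and group-by-time tests are independent, the chance of at least one false positive is 1 − 0.95² = 9.75%. Null simulations of the ANOVA gave 8.9% to 9.7%. Hence about 9-10%.

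**4. Any of three phases may decide.** For three equicorrelated two-sided tests at .05 (the documents give no correlations):

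| Assumed correlation | Chance of at least one false positive |
|---|---|
| 0 | 1 − 0.95³ = 14.3% |
| 0.3 | 13.6% |
| 0.5 | 12.5% |
| 0.7 | 10.9% |
| 0.9 | 8.4% |

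Readings from one patient in one sitting are unlikely to be uncorrelated, so 14.3% is a ceiling for three tests. At 0.7 to 0.9 the figure is about 8-11%.

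**5. The choice of effect changes the answer.** This step gives power under assumed effects, not error rates, for one session at 64 per arm with between-phase correlation r from 0.3 to 0.9.
- d = 0.5 in the during-session reading only: the pooled effect is (0.5/3)/√((1+2r)/3), which is 0.228 at r = 0.3 and 0.173 at r = 0.9. Power of the group test is 24.9% down to 16.2%. Group by phase has noncentrality 32 × 0.1667/(1−r) and power from 68.9% to over 99%. The two tests disagree in about 59-84% of trials.
- d = 0.5 equal in all phases: the group test has 97.0% down to 82.8%. Group by phase stays at 5%, because there is no interaction.

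**6. Secondaries under the same rule.** Table 2 lists eight instruments (Distress Thermometer, BPI, NRS, Perometer, bioimpedance, PSQI, ISI, BR23). With one test each at .05, the chance of at least one false positive is 1 − 0.95⁸ = 33.7% if independent, and 11.8% at an assumed correlation of 0.9.

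**7. Power of a single contrast.** Unadjusted t-test, d = 0.5: 80.1% at 64 per arm and 76.8% at 59 per arm (the 118 patients of section 9, divided by 2). Taking 10% off 118 gives 106, or 53 per arm, and 72.2%.

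**8. One worked choice: the mean of the three before-session readings in week 3, adjusted for the session-1 before reading.** The residual variance, in single-reading units, is (1+2rw)/3 − rb². Here rw is the correlation within week 3 and rb the correlation with baseline; both are assumed. At 59 per arm:
- Least favourable case, rw = 0.9 and rb = 0.3: 0.933 − 0.090 = 0.843. d = 0.5 becomes 0.5/√0.843 = 0.545, with power 83%. For d = 0.35 power is 54%.
- Most favourable case, rw = rb = 0.7: 0.800 − 0.490 = 0.310. d = 0.5 becomes 0.898, with power over 99%. For d = 0.35 power is 92%.

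**The case against.** The strongest reply is that the plan does have a hierarchy. One domain is primary and five are secondary, and naming vagal activity rules out HRV outputs that are not vagal. The sample size fits a between-group comparison, and the missing figure may state the test. A single omnibus ANOVA over all readings would also absorb much of the phase and session multiplicity.

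Most of this is fair, and it limits the point. It would be wrong to infer that the trial has no primary outcome, or that the missing figure is an omission. But the labels rank domains and do not choose among HRV tests. Nothing in the text points to the sample size figure for an index, phase or time point. An omnibus model still leaves the index and the deciding effect open, and step 3 applies to it.

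A reader might multiply out 27 or 45 separate tests and quote error rates of 75% or 90%. Those figures assume independent readings, each tested alone, and the plan does not say that this will be done. A reader might also infer that the analysts will pick a favourable result. The documents support only that the plan does not prevent a choice with results by arm in view; they say nothing about intent.

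Finally, adjusting secondaries for multiplicity is a matter of convention when they are labelled secondary, so its absence alone is not the fault. The fault is that the superiority wording extends to them.

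**Conclusion.** The point holds and should be fixed before data by arm are seen. The rule in section 14, applied as written to an HRV outcome with no fixed deciding contrast, does not hold the primary false-positive rate at 5%. The rate is about 9-10% if either of two ANOVA effects may decide. It is about 8-14% if any of three phases may, and 8-11% at the more plausible correlations of 0.7 to 0.9. More indices or time points would add to this.

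The omission is certain from the text. The sizes are illustrative: they rest on assumed correlations and on how many tests may carry the claim, and the documents give neither. The link between 128 and a single t-test is inferred.

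A reader might also conclude that a single contrast leaves only 72.2% power. That requires taking 10% off 118. Section 9 says drop-out was already taken into account in the sample size and the inclusion schedule, so 118 may be the number after drop-out. The 76.8% at 59 per arm is then the relevant figure.

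**What to change.** Replace the rule so that superiority rests on one primary HRV contrast at two-sided .05, fixed in writing before any data by arm are seen. The contrast should name:
- one vagal HRV index;
- one phase, or one defined within-session change;
- one time point or summary;
- the between-group effect, adjusted for the session-1 before reading, as the deciding test. For an acute contrast, adjust for the before reading of the same session, or take the contrast from session 1 only, so that acute and carried-over effects are not mixed.

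The mean of the before-session readings in week 3 is one workable choice, because patients on either radiotherapy duration reach it. An acute or whole-course contrast is equally open to the sponsor if fixed in advance. Report all other HRV readings and all secondary outcomes without a superiority claim. A multiplicity adjustment for the secondaries is optional.

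The change needs no new patients, visits or measurements. The other HRV readings and the secondaries lose the superiority claim. Power for one unadjusted contrast is as in step 7. The week-3 choice also leaves acute effects and the week 4-5 readings outside the claim, and its power at 59 per arm is about 83% to over 99% for d = 0.5 and 54-92% for d = 0.35 under the assumed correlations. Follow-up is not a further cost, because Table 2 schedules no HRV reading at follow-up.
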